8.1.3 Life-threatening

An adverse event or suspected adverse reaction is considered "life-threatening" if, in the view of either the investigator or sponsor, its occurrence places the patient or subject at immediate risk of death. It does not include an adverse event or suspected adverse reaction that, had it occurred in a more severe form, might have caused death. (21CFR312.32)

8.1.4 Severity

The severity of each Adverse Event will be assessed utilizing the CTCAE version 5.0.

8.1.5 Relationship to Study Product

All AEs will have their relationship to study product assessed using the terms: related or not related.

- Related There is a reasonable possibility that the study product caused the adverse event. Reasonable possibility means that there is evidence to suggest a causal relationship between the study product and the adverse event.
- Not Related There is not a reasonable possibility that the administration of the study product caused the event.

8.2 ASSESSMENT OF SAFETY EVENTS

AE information collected will include event description, date of onset, assessment of severity and relationship to study product and alternate etiology (if not related to study product), date of resolution of the event, seriousness and outcome. The assessment of severity and relationship to the study product will be done only by those with the training and authority to make a diagnosis and listed on the Form FDA 1572 as the site principal investigator or sub-investigator. AEs occurring during the collection and reporting period will be documented appropriately regardless of relationship. AEs will be followed through resolution.

SAEs will be:

- Assessed for severity and relationship to study product and alternate etiology (if not related to study product) by a licensed study physician listed on the Form FDA 1572 as the site principal investigator or sub-investigator.
- Recorded on the appropriate SAE report form, the medical record and captured in the clinical database.

• Followed through resolution by a licensed study physician listed on the Form FDA 1572 as the site principal investigator or sub-investigator.

For timeframe of recording adverse events, please refer to Section 6.1. All serious adverse events recorded from the time of first investigational product administration must be reported to the Sponsor with the exception of any listed in Section 8.4.

8.3 **Reporting of Serious Adverse Events**

Any AE that meets protocol-defined serious criteria or meets the definition of Adverse Event of Special Interest that require expedited reporting must be submitted immediately (within 24 hours of awareness) to OSRO Safety using the CCR SAE report form. Any exceptions to the expedited reporting requirements are found in Section **8.4**.

All SAE reporting must include the elements described in Section 8.2.

SAE reports will be submitted to the Center for Cancer Research (CCR) at: [contact] and to the CCR PI and study coordinator. CCR SAE report form and instructions can be found at: https://ccrod.cancer.gov/confluence/display/CCRCRO/Forms+and+Instructions

Following the assessment of the SAE by OSRO, other supporting documentation of the event may be requested by the OSRO Safety and should be provided as soon as possible.

8.4 WAIVER OF EXPEDITED REPORTING TO CCR

Death or Hospitalization that is deemed to be due to disease progression, and not attributable to the intervention will not be reported as an SAE. The event, and the assessment that it was caused by disease progression will be documented in the medical records. The causality assessment of Hospitalization will be re-evaluated any time when new information is received. If the causality assessment changes from disease progression to related to the study intervention, SAE report will be sent to the Sponsor immediately **in an expedited manner according to Section 8.3**. If there is any uncertainty whether the intervention is a contributing factor to the event, the event should be reported as AE or SAE as appropriate.

8.5 **Reporting Pregnancy**

All required pregnancy reports/follow-up to OSRO will be submitted to: [contact] and to the CCR PI and study coordinator. Forms and instructions can be found here: https://ccrod.cancer.gov/confluence/display/CCRCRO/Forms+and+Instructions.

8.5.1 Maternal Exposure

If a patient becomes pregnant during the course of the study, the study treatment should be discontinued immediately, and the pregnancy reported to the Sponsor no later than 24 hours of when the Investigator becomes aware of it. The Investigator should notify the Sponsor no later than 24 hours of when the outcome of the Pregnancy becomes known.

Pregnancy itself is not regarded as an SAE. However, congenital abnormalities or birth defects and spontaneous miscarriages that meet serious criteria (Section 8.1.2) should be reported as SAEs.

The outcome of all pregnancies (spontaneous miscarriage, elective termination, ectopic pregnancy, normal birth, or congenital abnormality) should be followed up and documented.

8.5.2 Paternal Exposure

Male patients should refrain from fathering a child or donating sperm during the study and for 60 days after the last dose of DAC-THU and pembrolizumab.

Pregnancy of the patient's partner is not considered to be an AE. However, the outcome of all pregnancies (spontaneous miscarriage, elective termination, ectopic pregnancy, normal birth, or congenital abnormality) occurring from the date of the first dose until 60 days after the last dose should, if possible, be followed up and documented.

8.6 REGULATORY REPORTING FOR STUDIES CONDUCTED UNDER CCR-SPONSORED IND

Following notification from the investigator, CCR, the IND sponsor, will report any suspected adverse reaction that is both serious and unexpected in expedited manner to the FDA in accordance to 21 CFR 31.2.32. CCR will report an AE as a suspected adverse reaction only if there is evidence to suggest a causal relationship between the study product and the adverse event. CCR will notify FDA and all participating investigators (i.e., all investigators to whom the Sponsor is providing drug under its INDs or under any investigator's IND) in an IND safety report of potential serious risks from clinical trials or any other source, as soon as possible, in accordance to 21 CFR Part 312.32.

All serious events will be reported to the FDA at least annually in a summary format.

8.7 SPONSOR PROTOCOL DEVIATION REPORTING

A Protocol Deviation is defined as any non-compliance with the clinical trial Protocol, Manual of Operational Procedures (MOP) and other Sponsor approved study related documents, GCP, or protocol-specific procedural requirements on the part of the participant, the Investigator, or the study site staff inclusive of site personnel performing procedures or providing services in support of the clinical trial.

It is the responsibility of the study Staff to document any protocol deviation identified by the Staff or the site Monitor in the CCR Protocol Deviation Tracking System (PDTS) online application. The entries into the PDTS online application should be timely, complete, and maintained per CCR PDTS user requirements.

In addition, any deviation to the protocol should be documented in the participant's source records and reported to the reviewing IRB per their guidelines. OSRO required protocol deviation reporting is consistent with E6(R2) GCP: Integrated Addendum to ICH E6(R1): 4.5 Compliance with Protocol; 5.18.3 (a), and 5.20 Noncompliance; and ICH E3 16.2.2 Protocol deviations.

9 CLINICAL MONITORING

Clinical site monitoring is conducted to ensure:

- that the rights of the participants are protected;
- that the study is implemented per the approved protocol, Good Clinical Practice and standard operating procedures; and
- the quality and integrity of study data and data collection methods are maintained.

Monitoring for this study will be performed by NCI CCR Office of Sponsor and Regulatory Oversight (OSRO) Sponsor and Regulatory Oversight Support (SROS) Services contractor. Clinical site monitoring activities will be based on OSRO standards, FDA Guidance E6(R2) Good

Clinical Practice: Integrated Addendum to ICH E6(R1) March 2018, and applicable regulatory requirements.

Details of clinical site monitoring will be documented in a Clinical Monitoring Plan (CMP) developed by OSRO. CMPs will be protocol-specific, risk-based and tailored to address human subject protections and integrity of the study data. OSRO will determine the intensity and frequency of monitoring based on several factors, including study type, phase, risk, complexity, expected enrollment rate, and any unique attributes of the study and the site. The Sponsor will conduct a periodic review of the CMP to confirm the plan's continued appropriateness. A change to the protocol, significant or pervasive non-compliance with GCP, or the protocol may trigger CMP updates.

OSRO SROS Monitoring visits and related activities will be conducted throughout the life cycle of each protocol. The first activity is before the study starts to conduct a Site Assessment Visit (SAV) (as warranted), followed by a Site Initiation Visit (SIV), Interim Monitoring Visit(s) (IMVs), and a study Close-Out Visit (COV).

Some monitoring activities may be performed remotely, while others will occur at the study site(s). Monitoring visit reports will describe visit activities, observations, and associated action items or follow-up required for resolution of any issues, discrepancies, or deviations. Monitoring reports will be distributed to the study PI, NCI CCR QA, CCR Protocol Support Office, coordinating center (if applicable), and the Sponsor regulatory file.

The site Monitor will inform the study team of any deviations observed during monitoring visits. If unresolved, the Monitor will request that the site Staff enter the deviations in the CCR Protocol Deviation Tracking System (PDTS) for deviation reporting to the Sponsor and as applicable per institutional and IRB guidance.

10 STATISTICAL CONSIDERATIONS

The primary objectives of this trial are to determine the objective response rates of DAC/THU plus pembrolizumab in patients with NSCLC, EsC, and MPM who have intra-tumoral PD-L1 expression of at least 50% and those who do not. Approximately 30% of NSCLC exhibit PD-L1 expression in 50% or more cancers cells, another 30-50% have PD-L1 expression in 1-49% of cancer cells, and the remaining NSCLC have no PD-L1 expression by IHC (25, 111-113). In contrast, 20-40% of gastroesophageal cancers exhibit PD-L1 expression (25, 111, 112); in the majority of these cancers, PD-L1 is expressed at low levels, and tends not to be expressed on the cancer cells (112). Despite these differences regarding PD-L1 expression, present data indicate that responses to immune checkpoint inhibitors in EsC are comparable to NSCLC with low PD-L1 expression (114). Approximately 25%-30% of MPM exhibit some level of PD-L1 expression, with the expression being primarily on tumor-associated immune cells (115). PD-L1 expression tends to be higher on sarcomatoid MPM and lower on the more common epithelioid subtype. Response rates in MPM following PD-1 blockade are comparable to NSCLC with similar levels of PD-L1 expression (99, 100).

Patients will be initially enrolled onto a multi-dose level dose escalation portion of the trial following a 3+3 design. Patients will not be stratified for the Phase I component, which will accelerate our ability to define MTD. Thus, for the dose escalation phase, up to 6 patients per dose level may be enrolled, with a total of 12 patients required with a maximum of 2 dose levels. At the MTD, an additional 4 patients will be enrolled to further estimate the safety of the combination.

Since published data have demonstrated a response rate of 45% for first-line pembrolizumab alone in NSCLC patients with PD-L1 expression of 50% or greater (95), (98), this trial will try to demonstrate if a response rate in excess of 45% may be realized in NSCLC patients with \geq 50% PD-L1 expression by the addition of DAC/THU. Briefly, NSCLC patients with high intratumoral (50% or greater) PD-L1 expression will be evaluated for response as part of a Simon optimal twostage Phase II trial design (116) in order to rule out an unacceptably low PR+CR rate of 35% (p0=0.35) in favor of an improved response rate of 60% (p1=0.60). With alpha=0.10 (probability of accepting a poor treatment=0.10) and beta=0.20 (probability of rejecting a good treatment=0.20), the first stage will determine the response rate in 10 evaluable patients, including those NSCLC patients among the 10 who are treated at the MTD from the Phase I cohort who have high intra-tumoral PD-L1 expression. If 0 to 4 of the 10 patients have a clinical response, then no further patients will be accrued. If 5 or more of these 10 patients have a response, then accrual would continue until a total of 23 evaluable patients have been treated at the MTD. As it may take up to several months to determine if a patient has experienced a response, a temporary pause in the accrual may be necessary to ensure that enrollment to the second stage is warranted. If there are 5 to 10 patients with a response out of 23 patients, this would be an uninterestingly low response rate. If there were 11 or more of 23 (47.8%) who experienced a response, this would be sufficiently interesting to warrant further study in later trials. Under the null hypothesis (35% response rate), the probability of early termination is 75.2%.

NSCLC patients with low (0-49%) intratumoral PD-L1 expression will be evaluated for response using a Simon optimal two-stage Phase II trial design (116) in order to rule out an unacceptably low PR+CR rate of 10% (p0=0.10) in favor of an improved response rate of 30% (p1=0.30). Variable mutational burdens among NSCLC with low PD-L1 expression could affect responses to immune checkpoint inhibitors, potentially making this cohort more heterogeneous than the NSCLC high PD-L1 expresser cohort. For example, NSCLC patients without activating mutations in EGFR, HER2 or ALK with PD-L1 tumor proportion score (TPS) < 1% have an expected response rate of less than 10%, whereas those with activating mutations involving these genes have response rates of 5% or less; patients with PD-L1 TPS of 1-49% have a 17% response rate (25, 103, 104, 113). Therefore, with alpha=0.05 (probability of accepting a poor treatment=0.05) and beta = 0.20 (probability of rejecting a good treatment=0.20), the first stage will determine the response rate in 10 evaluable patients, including those among the 10 who are treated at the MTD from the Phase I cohort who have low intra-tumoral PD-L1 expression, and if 0 to 1 of the 10 have a clinical response, then no further patients will be accrued. If 2 or more of these 10 patients have a response, then accrual would continue until a total of 29 evaluable patients have been treated in this cohort. As it may take up to several months to determine if a patient has experienced a response, a temporary pause in the accrual may be necessary to ensure that enrollment to the second stage is warranted. If there are 2 to 5 patients with a response out of 29 patients, this would be an uninterestingly low response rate. If there were 6 or more of 29 (20.7%) who experienced a response, this would be sufficiently interesting to warrant further study in later trials. Under the null hypothesis (10% response rate), the probability of early termination is 73.6%.

While accrual of NSCLC patients is underway, up to 10 EsC patients including any from the Phase I component after the MTD has been identified, will be accrued to examine responses in EsC patients treated with DAC-THU at the MTD and pembrolizumab. Since it is anticipated that most if not all of these 10 patients will have low or no PD-L1 expression in their tumor tissues, and because response rates to immune checkpoint inhibitors in EsC appear to be comparable to NSCLC with low PD-L1 expression, criteria similar to those reported for the NSCLC low PD-L1 cohort

will be used to identify a potential signal of activity. Specifically, if there are 2 or more responses in these 10 patients, this might warrant amendment of the current protocol to enable expansion of this cohort with appropriate statistical criteria, or to justify a larger, focused Phase II trial.

Additionally, up to 10 MPM patients including any from the Phase I component after the MTD has been identified, will be accrued to examine responses in MPM patients treated with DAC-THU at the MTD and pembrolizumab. Since it is anticipated that most if not all of these 10 patients will have low PD-L1 expression in their tumor tissues, and because response rates to immune checkpoint inhibitors in MPM patients appear to be comparable to NSCLC with low PD-L1 expression, criteria similar to those reported for the NSCLC low PD-L1 cohort will be used to identify a potential signal of activity. Specifically, if there are 2 or more responses in these 10 patients, this might warrant amendment of the current protocol to enable expansion of this cohort with appropriate statistical criteria, or to justify a larger, focused Phase II trial.

It is expected that approximately 2-4 patients per month may enroll onto this trial. Thus, it is expected that 24-30 months may be required in order to enroll up to 78 evaluable patients. Assuming two dose levels will be used to define MTD, the Phase I component of the trial will require 16 patients. The Phase II portion of the trial may require 29 NSCLC patients for the PD-L1 high, and 23 NSCLC patients for the PD-L1 low cohorts, plus 10 EsC patients, plus 10 MPM patients, less 10 patients treated at the MTD in the Phase I portion of the protocol; hence 16+29+23+10+10-10=78 patients In order to allow for a small number of inevaluable patients, the accrual ceiling will be set at **85** patients, acknowledging that the trial can be completed with 60 or fewer patients if response goals for each cohort are not met.

Twelve months after Amendment E has been implemented, accrual will be assessed. If the trial is not on track for accrual targets, e.g., if fewer than 12 patients have been accrued within 12 months, the protocol will either be terminated, or the trial will be opened at an additional site to accelerate patient accrual, and ensure timely completion of this trial.

will Pharmacokinetic analysis be conducted using non-compartmental methods. Pharmacodynamic analyses, as well as analyses of molecular endpoints in tumor tissues and PBMC before and after treatment will be performed, with the primary focus being with respect to results at the MTD. For pharmacodynamic endpoints, descriptive statistics will be used for each endpoint. Briefly, pharmacodynamic and molecular endpoints in target tissues will be assessed before and after DAC-THU/pembrolizumab treatment, with the primary focus being comparison of microarray, gRT-PCR and IHC results relative to profiles identified in our preclinical studies. It is anticipated that non-parametric statistical methods will be used to compare paired results before and after treatment (but not between groups), as well as to perform comparisons or correlations among parameters. As the exact set of comparisons and analyses to be performed will be determined following completion of the trial and will be based on limited numbers of patients, the analyses will be considered exploratory and hypothesis generating rather than definitive.

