2.3.1 Treatment Assignment Procedures

Cohorts

Number	Name	Description
1	Dose-Escalation	Subjects enrolled to dose escalation cohorts
2	Dose Expansion: NSCLC with high PD-L1	NSCLC subjects with high PD-L1 tumor expression enrolled at the MTD after the MTD is established
3	Dose Expansion: NSCLC with low PD-L1	NSCLC subjects with low PD-L1 tumor expression enrolled at the MTD after MTD is established
4	Dose Expansion: EsC	EsC subjects enrolled at the MTD after MTD is established
5	Dose Expansion: MPM	MPM patients enrolled at the MTD after MTD is established

Arms

Number	Name	Description
1	Dose Escalation	DAC-THU + pembrolizumab at escalating doses
2	Dose Expansion	DAC-THU + pembrolizumab at the dose established in Arm 1

Arm Assignment

Subjects in Cohort 1 will be assigned to Arm 1.

Subjects in Cohort 2, Cohort 3, Cohort 4 and Cohort 5 will be assigned to Arm 2.

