3.1.3 Dose Escalation

The revised dosing regimen selected for this trial is based on pharmacodynamic evidence of systemic hypomethylation without significant systemic toxicities mediated by oral DAC-THU in patients with sickle cell disease in a recent Phase 1 clinical trial (108), as well as experience with DAC-THU/Pembrolizumab in NSCLC (Section 1.2.11.2). The frequency of DAC-THU dosing will increase using a conventional 3+3 Phase I study design attempting to maximize systemic DNMT1 depletion while avoiding Grade 3 or greater systemic toxicities (primarily neutropenia/thrombocytopenia). *Due to the uncertainty regarding cumulative toxicities, no intrapatient escalation will be allowed.*

Dose escalation will proceed as indicated in **Table 7** using three patients per dose level (irrespective of Tumor PD-L1 expression) until DLT within the first 6 weeks (two cycles) of DAC-THU therapy is observed. If one of three patients at any given dose level experiences DLT, up to three additional patients will be treated at this dose level. If only one of six patients exhibit DLT, subsequent patients will be enrolled into the next higher dose level. As soon as two patients at any given dose level develop DLT, no additional patients will be entered at that level. Subsequent patients will be accrued into the preceding dose level; if DLT is observed in less than two of six patients treated at this lower level, this dose will represent maximum tolerated dose (MTD).

Table 7: DAC-THU Dosing Schema for High (50% or Greater) and Low (0-49%) PD-L1
Expression Groups

Dose Level	DAC	DAC	THU	THU	Frequency^
	mg/kg/course	mg/kg/day*	mg/kg/course	mg/kg/day*	wk 1,2,4,5,7,8
-1	2.0	0.17	120	10	T;W
1	2.5	0.21	120	10	T;W
2	3.0	0.25	120	10	T;W
*on days a	administered				
^ T: Tuesd	lay; W: Wednesday				

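### The maximum of 78 patients assumes two dose levels and full re-use of the ten MTD patients; Table 7 and the cohort rules allow up to 84 if either assumption fails, and 90 only if both do

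*Combined protocol and SAP*

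**What the plan says.** **Phase I size.** Section 10 allows as many as six patients at each level, "with a total of 12 patients required with a maximum of 2 dose levels". It then adds the expansion: "At the MTD, an additional 4 patients will be enrolled to further estimate the safety of the combination". The accrual paragraph of Section 10 repeats the premise: "Assuming two dose levels will be used to define MTD, the Phase I component of the trial will require 16 patients".

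**Total.** The same paragraph adds the Phase II cohorts, removes the ten MTD patients, and concludes "hence 16+29+23+10+10-10=78 patients". The accrual ceiling is 85, and the difference is meant to cover a small number of inevaluable patients.

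**Dose levels.** Table 7 in Section 3.1.3 lists three levels: -1, 1 and 2. Two DLTs close a level, and then: "Subsequent patients will be accrued into the preceding dose level". The lower level becomes the MTD if fewer than two of six patients there have a DLT.

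**Who is counted twice.** The sections differ:
- The Précis and Section 3.1 fold all ten MTD patients into the NSCLC first-stage counts.
- The NSCLC paragraphs of Section 10 count those of the ten who have NSCLC with the relevant PD-L1 level.
- For EsC, Section 10 counts "up to 10 EsC patients including any from the Phase I component after the MTD has been identified"; the MPM sentence is parallel. Section 3.1 likewise refers to patients in the Phase I expansion.
- The cohort table in Section 2.3.1 describes Cohort 2 as "enrolled at the MTD after the MTD is established", describes Cohorts 3 to 5 in the same way, and places escalation patients in Cohort 1.

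**The concern.** A maximum sample size should hold on every path the design permits. This one rests on two favourable conditions: that no more than two dose levels are used, and that every patient treated at the MTD is used again in a Phase II cohort. Table 7 contradicts the first as a stated maximum. The second fails whenever an EsC or MPM patient is among the escalation patients at the dose that becomes the MTD, and Phase I is open to all three diseases.

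What is at stake is the allowance for inevaluable patients. Section 6.3.2 replaces patients who electively stop before nine weeks, and treats those who progress between three and nine weeks as not evaluable for response, so the spare places are likely to be needed. It is also better to settle which Phase I patients belong to each cohort before their responses are known.

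**Working it through.** **1. Reproduce the plan's figures.**
- Escalation: 6 × 2 = 12. With expansion: 12 + 4 = 16.
- Phase II: 29 + 23 + 10 + 10 = 72.
- Total: 16 + 72 - 10 = 78. Allowance: 85 - 78 = 7.

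All agree with Section 10. The accrual paragraph attaches 29 to the high and 23 to the low PD-L1 cohort, the reverse of the design paragraphs; the sum is unaffected.

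**2. Largest escalation under Section 3.1.3.** No starting level is stated; I assume level 1, as the numbering suggests. One permitted path is:
- level 1: 0 of 3 with DLT (3 patients)
- level 2: six patients, two or more DLTs (6)
- level 1 again: three more, two or more DLTs (3)
- level -1: six patients, fewer than two DLTs, so this is the MTD (6)

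That is 3 + 6 + 3 + 6 = 18, or 18 + 4 = 22 with the expansion. Full enumeration of the 3+3 paths found no larger number.

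**3. Overlap.** With six escalation patients at the MTD, ten patients are treated there. Let u be the number of those six who join no Phase II cohort. The overlap is 10 - u. Under Section 10, u is the number with EsC or MPM. Under a literal reading of Section 2.3.1, u = 6 whatever the disease.

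**4. Totals.** Total = Phase I + 72 - overlap.

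| Escalation | Overlap | Total | Spare under 85 |
|---|---|---|---|
| 12 | 10 | 16 + 72 - 10 = 78 | 7 |
| 18 | 10 | 22 + 72 - 10 = 84 | 1 |
| 12 | 4 | 16 + 72 - 4 = 84 | 1 |
| 18 | 9 | 22 + 72 - 9 = 85 | 0 |
| 18 | 8 | 22 + 72 - 8 = 86 | -1 |
| 18 | 4 | 22 + 72 - 4 = 90 | -5 |

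A three-level path with 15 escalation patients (3 + 3 + 3 + 6) also ends with an MTD; it passes 85 only at an overlap of 5 or fewer (19 + 72 - 5 = 86).

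**5. How likely is the three-level path?** The documents give no DLT rates, so these are assumptions. For rates of 10/20/30% at levels -1/1/2:
- level 1, 0 of 3: 0.8³ = 0.512
- level 2, one of three and then at least one of three: 0.441 × 0.657 = 0.290
- level 1, at least two of three more: 0.104
- level -1, fewer than two of six: 0.886

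Product: 0.512 × 0.290 × 0.104 × 0.886 = 0.0137.

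| DLT rates, levels -1/1/2 | P(three levels used) | P(18 patients and an MTD found) |
|---|---|---|
| 5/10/20% | 0.006 | 0.004 |
| 10/20/30% | 0.027 | 0.014 |
| 10/30/50% | 0.061 | 0.022 |
| 20/40/60% | 0.070 | 0.013 |

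**6. Both NSCLC cohorts must also pass stage 1 for the maximum to be reached.** The stopping probabilities are 0.7515 (high PD-L1) and 0.7361 (low) at the null rates, and 0.1662 and 0.1493 at the target rates. If the cohorts are independent, both continue with probability 0.2485 × 0.2639 = 0.066 at the null rates and 0.8338 × 0.8507 = 0.709 at the targets. If this is also independent of the DLT results, the 18-patient route to 84 or more has probability of at most about 0.0215 × 0.709 = 0.015 in these scenarios.

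**The case against.** The strongest defence is that nothing is added up wrongly. The accrual paragraph states its two-level assumption openly, levels 1 and 2 read as the planned escalation with -1 as a fallback, and 78 follows. This stands for the accrual paragraph. It does not cover the earlier sentence in Section 10, which calls two levels a maximum.

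Three stronger readings are tempting, and the documents do not support them.
- *Only the four expansion patients are sure to count.* This follows from Section 2.3.1 read alone. But that is a registration table, and the Précis, Section 3.1 and the NSCLC paragraphs of Section 10 expressly bring in patients treated at the MTD. Under Section 10, an overlap of 4 requires all six escalation patients at the MTD to have EsC or MPM.
- *The stage-1 denominators are uncertain.* They are not: Section 10 fixes them at ten evaluable patients in each NSCLC cohort. What is unsettled is which patients may fill those places.
- *The ceiling will be broken.* Neither failure alone does this; each gives at most 84.

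The defence may add that the three-level path is rare. Under the assumed rates and a start at level 1, it is. The overlap problem does not depend on that path, but the documents give no disease mix for Phase I, so its probability cannot be calculated.

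**Conclusion.** The point holds as a minor inconsistency in the stated sample size. As a maximum, two dose levels and 12 escalation patients disagree with Table 7, which permits 18 (22 with the expansion). The subtraction of ten disagrees with the EsC and MPM counting rule in Section 10 and with the cohort table in Section 2.3.1.

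Either failure alone raises the maximum from 78 to at most 84 and cuts the inevaluable allowance from 7 to as few as 1. Only the two together exceed 85: with three full levels this needs an overlap of 8 or fewer, and 90 is the worst case. The maxima assume that both NSCLC cohorts pass stage 1 and that the EsC and MPM cohorts fill. The probabilities rest on assumed DLT rates and a start at level 1; another start could change them. The Simon boundaries are unaffected.

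**What to change.** 1. In Section 10, replace the two-level maximum with one that agrees with Table 7: 18 escalation patients, 18 + 4 = 22 for Phase I. If 16 is kept as the expected case, label it so.
2. Adopt one prespecified rule for which Phase I patients treated at the MTD may fill the ten first-stage places in each cohort, and word Sections 2.3.1, 3.1 and 10 and the Précis to match. The rule should say whether an escalation patient must also meet the cohort's own entry criteria, since Section 2.1.1 sets a prior-therapy condition for Cohort 3 that it does not set for Cohort 1.
3. Restate the maximum and the allowance under that rule. If all MTD patients count, the maximum is 78 to 84 and the allowance 7 to 1. If only expansion patients count, it is 84 to 90 and the allowance 1 to -5, so the ceiling would need to be reconsidered.
4. Correct the exchanged 29 and 23 labels in the accrual paragraph at the same time.

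The cost is wording only. No dose, boundary or procedure changes; the stated margin becomes less comfortable.
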